3.0 Protocol Objectives

The main objective of this study is to collect safety data to examine whether MDMA-assisted therapy will be tolerated and to estimate effect size of symptom reduction in social anxiety that is common in the adult autistic population as evaluated by standard clinical measures.

3.1 Primary Objective:

To estimate effect sizes of social anxiety symptom reduction between MDMA and placebo, as measured by the clinician-administered LSAS administered by a blinded IR, at baseline, one day, two weeks, and one month after each experimental session, and at 6-month follow-up.

3.2 Secondary Objectives:

The following objectives will compare MDMA subjects to placebo subjects in Stage 1:

- To assess effects on levels of OT, AVP, and CORT in peripheral blood at baseline, once during each experimental session between hours 2 – 3, one month after the second experimental session, and at 6-month follow-up.
- To assess effects on social perception using The Awareness of Social Inference Test (TASIT) at baseline, once during each experimental session between hours 2 – 3, one month after the second experimental session, and at 6-month follow-up.
- To assess effects on emotion labeling using the Toronto Alexithymia Scale-20 (TAS-20) at baseline, one month after each experimental session, and 6-month follow-up.
- To assess effects on emotion regulation using the Emotion Regulation Questionnaire (ERQ) at baseline, one month after each experimental session, and 6-month follow-up.
- To assess effects on depression symptoms as measured by the Beck Depression Inventory-II (BDI-II) at baseline, one day, two weeks, one month after each

- experimental session, monthly by mail during the 5 months leading up to the 6-month follow-up assessment.
- To assess effects on perceptions of stress as measured by the Perceived Stress Scale (PSS) at baseline, within 24 hours after each experimental session, one month after each experimental session and monthly by mail leading up to the 6-month follow-up assessment.
 - To assess effects on four aspects of empathy, as measured by the Interpersonal Reactivity Index (IRI) at baseline, within 24 hours after each experimental session, one month after each experimental session, and at the 6-month follow-up assessment.

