The PSS is a 10-item self-report measure that is widely used in research to assess stress in persisting conditions and takes about 1 – 2 minutes to complete. The PSS includes six negative items that are intended to assess lack of control and negative affective reactions and four positive items that measure the degree of ability to cope with existing stressors. Individuals indicate how often they felt or thought a certain way during the last month (0 = *never*, 4 = *very often*). The PSS was correlated with depressive symptomatology and social anxiety in TD populations [134]. The PSS will be completed according to the Time and Events table.

The IRI assesses four aspects of empathy: social functioning, self-esteem, emotionality, and sensitivity to others [135-137]. Empathy is not a discrete emotion. More accurately, empathy is a set of constructs. Therefore, the IRI accounts for the fact that each construct concerns an individual's responses to the observed experiences of other people, yet each construct is distinctive from the others. The self-report questionnaire includes 28 items that are rated on a 5-point, Likert-type scale. The four 7-item subscales include two measures of cognitive empathy and two measures of affective empathy. The internal reliabilities for the four scales range from .71 to .77, and test-retest reliabilities range from .62 to .71 [135]. One study [138] administered the IRI to 21 adults with Asperger's Syndrome and to 21 matched controls. As anticipated, the Asperger's group scored lower on the measures of cognitive empathy, but they scored similarly to controls on the Empathic Concern scale, and scored higher than controls on the Personal Distress scale. In the absence of an abundance of robust validity testing of empathy assessments with adult autistic populations, the IRI provides a good option for a multidimensional assessment of empathy factors. The IRI will be completed according to the Time and Events table.

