- integration, as needed.
- cc. Spontaneously reported reactions, AEs, and concomitant medications will be collected, as described in Section 8.5 and Section 9.0.
 - dd. Assess status of symptoms at baseline specific to the study population.
 - ee. After the experimental sessions, an overnight stay at a hotel located close to the site will be offered to subjects, accompanied by their support partners, if they live further than 30 miles from the site.
 - ff. During the night of the experimental session, subjects will be given the following measures to complete prior to the integrative session on the next day:
 - a. RSES
 - b. IRI
 - c. PSS

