5.2.6 Biweekly Integrative Sessions

In addition to the integrative session the morning after each experimental session, the subject will have two additional integrative sessions with the therapists lasting 60 minutes

with the therapists between each experimental session scheduled at two-week intervals following the last integrative session. The therapists may conduct more or longer integrative sessions if they and the subject deem it necessary.

Activities for these sessions include integration of material that emerged as a part of experimental sessions and afterward into daily life. Therapists will emphasize their commitment to support the subject during the integration period and will be available via phone or pager.

During integrative sessions:

- a. Record each integrative session to audio and video. Subjects may receive access to copies of the recordings on a secure, password-protected website upon request.
- b. The C-SSRS will be administered just prior to beginning each integrative session.
- c. General wellbeing will be assessed at each integrative session.
- d. The subject and therapists will continue to work on supporting the subject as she or he considers his or her experiences during experimental sessions.
- e. The therapists will use clinical judgment to assess the subject's psychological wellbeing during this period of time. If there are any indications of continuing anxiety or distress, the therapists may arrange to work on reducing the distress at a specially scheduled integrative session, through continuing contact, or at the next regularly scheduled integrative session. The subject may also initiate contact with the therapists at any time throughout the study.
- f. At the second integrative session after the second experimental session, blood will be drawn for biomarker analysis.
- g. At the second integrative session after the second experimental session, collect information on phase of menstrual cycle for female subjects.
- h. At the beginning or end of each integrative session, subjects will complete:
 - a. BDI-II
 - b. STAI
- i. At the beginning or end of each integrative session, the IR will administer the LSAS.
- j. At the beginning or end of the third integrative session, subjects will also complete:
 - a. ERQ
 - b. TAS-20
 - c. TASIT
- k. Spontaneously reported reactions, AEs, and concomitant medications will be collected, as described in Section 8.5 and Section 9.0.

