The main estimates of effect size from blinded data will be conducted after the outcome measure assessments at the six-month follow-up are complete for all subjects. Data from all doses of MDMA during Stage 1 (n=16), to be compared with all data from placebo sessions (n=8), with each experimental session treated as an independent observation. The MDMA condition will encompass both Group 1 and Group 2 MDMA doses. Estimates of effect size will be obtained from BDI-II, STAI, PSS, IRI, RSES, ERQ, TAS-20, and QoL-Q scores collected pre-treatment, during and after each experimental session, and the follow-up period, with p value set at 0.05. Effect size will be used to determine the appropriate sample size for future studies.

Scores for BDI-II, STAI, PSS, IRI and RSES completed after each of the experimental session will be averaged to produce mean scores for these periods, including a post-experimental session 1 and post-experimental session 2 average score. BDI-II, STAI and PSS scores gathered via postal mail at monthly intervals from two to five months after the second experimental session will be averaged to produce mean scores for the follow-up period. Missing responses will be replaced with the sample average. These averages will be used for estimates of effect size.

TASIT scores will be compared assessing baseline, after experimental session 1, after experimental session 2, at integrative session six and at 6-month follow up. Correlations between TASIT scores and LSAS scores at the time point following each TASIT score will be made to see whether increased awareness of social cues is associated with reduced social anxiety. MDMA dose will be used as a covariate in order to examine the potential relationship between dose and changes in one or more variable, with dose (75, 100 or 125 mg) serving as the covariate.

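### Objectives, Table 2 and section 5.2.6 disagree on the one-month questionnaires after session 1; under Table 2 the post-session-1 PSS mostly describes the month before the first dose

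*Protocol*

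**What the plan says.** - **Objectives.** Protocol 3.2 has the PSS "within 24 hours after each experimental session, one month after each experimental session and monthly by mail leading up to the 6-month follow-up assessment". It treats the IRI alike: "Interpersonal Reactivity Index (IRI) at baseline, within 24 hours after each experimental session, one month after each experimental session". RSES has the same two post-session time points. ERQ and TAS-20 are placed one month after each session. SAP 3.2 repeats all of this.
- **Governing schedule.** Protocol 5.1.2 states: "The PSS will be completed according to the Time and Events table". It says the same of IRI, RSES, ERQ and TAS-20.
- **Table 2 (Stage 1).** None of the five scales is ticked at V9. BDI-II and STAI are.
- **Overnight forms.** On the night of each session, per 5.2.3, "subjects will be given the following measures to complete prior to the integrative session on the next day"; the list is RSES, IRI and PSS.
- **Visit text, 5.2.6.** The item reads "At the beginning or end of the third integrative session, subjects will also complete", followed by ERQ, TAS-20 and TASIT. BDI-II, STAI and LSAS are listed for every biweekly session. PSS, IRI and RSES are not listed at all.
- **PSS recall, 5.1.2.** "Individuals indicate how often they felt or thought a certain way during the last month".
- **Analysis.** Protocol 12.0 says: "Scores for BDI-II, STAI, PSS, IRI and RSES completed after each of the experimental session will be averaged to produce mean scores". It forms one average per session and uses these for effect-size estimates. SAP 8.10.2 instead tests change from baseline to V13.

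**The concern.** Two problems meet here. The first is a contradiction: a site that follows Table 2 cannot deliver the one-month post-session-1 data that the objectives name, and a site that follows the 5.2.6 list could also miss PSS, IRI and RSES at V13, where Table 2 ticks them and the SAP analyses them.

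The second concerns PSS alone. A form with one-month recall, completed the night after dosing, looks back almost entirely at time before that dose. If V7 is the only PSS after session 1, the score that section 12.0 labels as post-session 1 has little opportunity to reflect session 1. The V11 form, labelled as post-session 2, looks back mainly at the month after session 1.

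At stake are the section 12.0 effect sizes for PSS, which are meant to inform the size of later studies, and any reading of PSS by dose. Section 12.0 treats each session as an independent observation, so session 1 supplies half of them: 8 of 16 for MDMA and 4 of 8 for placebo.

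**Working it through.** The plan gives no figure of its own to reproduce. The check is a reading of Table 2 by column, followed by calendar arithmetic.

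**Step 1. Ticks in protocol Table 2**

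| Scale | Ticked at | Between session 1 (V6) and session 2 (V10) |
|---|---|---|
| PSS | V3, V7, V11, V13, monthly mail, V14 | V7 only |
| IRI, RSES | V3, V7, V11, V13, V14 | V7 only |
| ERQ, TAS-20 | V5, V13, V14 | none |
| BDI-II, STAI (for comparison) | V3, V7, V8, V9, V11, V12, V13, mail, V14 | V7, V8, V9 |

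Table 3 repeats the gap for PSS, IRI and RSES in Stage 2: V16, V20 and V22, not V18.

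**Step 2. Share of the V7 PSS window before the first dose**

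Inputs: recall of one month, taken as R = 28 to 31 days (assumption); form completed h = 12 to 24 hours after the dose (assumption, from a dose at about 10:00 and completion before the next-day visit).

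Share before the dose = 1 − (h/24)/R

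| R (days) | h = 12 | h = 24 |
|---|---|---|
| 28 | 98.2% | 96.4% |
| 30 | 98.3% | 96.7% |
| 31 | 98.4% | 96.8% |

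**Step 3. V11 and V13 windows (R = 30, forms at 24 hours for V11)**

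- V11: 1/30 = 3.3% lies after session 2. The other 29/30 = 96.7% lies between sessions 1 and 2, for any gap between sessions of 29 days or more.
- V13: 1 + 14 + 14 = 29 days after V10, so 29/30 = 96.7% lies after session 2.

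**Step 4. What the section 12.0 scores cover**

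- Post-session 1 is V7 alone: 3.3% of the window follows session 1.
- Post-session 2 is the mean of V11 and V13: (1/30 + 29/30)/2 = 50% follows session 2, and the other 50% lies between the sessions.

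**Step 5. Link to dose**

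In Stage 1 (Table 1), 75 mg is given only in session 1 and 125 mg only in session 2; 100 mg is given in session 2 for Group 1 and in session 1 for Group 2. Assume each session average is assigned to that session's dose. The share of the window that follows any MDMA is then:

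- 75 mg: 3.3%
- 100 mg: (4 × 3.3% + 4 × 100%)/8 = 51.7%
- 125 mg: 100%

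The order matches the dose order, so a PSS-by-dose plot could show a trend that comes from timing alone.

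**Step 6. Would adding V9 be enough?**

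V9 falls 29 days after V6, so 1/30 of its window precedes the dose. Averaged with V7, as section 12.0 would require, the pre-drug share is (29/30 + 1/30)/2 = 50%. V9 needs to stand alone.

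**The case against.** Several stronger readings are tempting, and the documents do not support them.

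- **A reader might infer that the trial deliberately measures PSS, IRI and RSES only within 24 hours of session 1.** The objectives in both documents also place them one month after it. Table 2 allots V9 2.1 hours against 1.7 for V8, although V9 has no tick that V8 lacks. This suggests, without proving it, that the forms were budgeted at V9 and the ticks left out. The defect is an inconsistency rather than a chosen design.
- **A reader might infer that ERQ and TAS-20 will have no data one month after session 1.** That holds under Table 2, but 5.2.6 is ambiguous. Its blood-draw and menstrual-phase items are expressly limited to the time after the second experimental session; its ERQ/TAS-20 item is not. Section 12.0 speaks of a sixth integrative session, and on that numbering the third is V9. Against this, the same item lists TASIT, which the objectives do not place at V9.
- **A reader might infer that a session-1 effect d1 would appear as about 0.03 × d1, and that the post-session-2 score equals (d1 + d2)/2.** This needs every recalled day to count equally and no carry-over from session 1 into the second month. The documents support neither, and a respondent's state on the night after dosing may colour the answers.
- **A reader might extend the recall argument to IRI and RSES.** The documents give no recall window for either.

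The strongest remaining objection is narrow impact. SAP 8.10.2 tests baseline to V13, and SAP 8.10.2.1 tests V13 to six months; neither uses V7, V11 or the session averages. PSS is one of many exploratory secondary scales in a trial of 8 versus 4 subjects, and the LSAS is untouched. That limits the weight of the point. It does not remove the contradiction, or the section 12.0 rule that assigns V7 and V11 to the wrong periods.

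**Conclusion.** The point holds in this form. Five scales lack a V9 tick that the objectives require, and 5.2.6 leaves PSS, IRI and RSES out of the one-month visits, V13 included. Under Table 2, 96–98% of the recall window of the only post-session-1 PSS precedes the first dose, and about 97% of the V11 window lies between the two sessions. Section 12.0 therefore ties PSS scores to the wrong session, and through session to the wrong dose.

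The percentages assume a month of 28–31 days (30 for V11) and completion 12–24 hours after dosing (24 for V11). They describe the calendar, not how far an effect would shrink. The check rests on the protocol's Table 2, because the SAP's Stage 1 table was not legible in the text available. The SAP's V13 tests stand provided the site follows Table 2 at V13. This should be corrected, but it does not threaten the primary analysis.

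**What to change.** 1. In Table 2, tick PSS, IRI, RSES, ERQ and TAS-20 at V9, before the V10 dose, in line with objectives 3.2.
2. In 5.2.6, list PSS, IRI and RSES for the one-month sessions (V9 and V13), and state which visits the ERQ/TAS-20/TASIT item covers.
3. In 12.0, use V9 PSS as the session-1 score and V13 PSS as the session-2 score, without averaging in V7 or V11.
4. Keep the within-24-hour PSS, IRI and RSES, which are named objective time points, but report them separately from the one-month scores.
5. If data were already collected under Table 2, do not present V7 PSS as a session-1 effect. Show V11 PSS, in a labelled sensitivity analysis, as mainly covering the month after session 1.

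Cost: wording changes and extra forms at an existing visit. From the completion times in 5.1.2, PSS 1–2, RSES 1–2, ERQ 4–6 and TAS-20 5–10 minutes sum to 11–20 minutes, plus the 28-item IRI, for which no time is given. V9 already has 0.4 hours (24 minutes) more than V8, so most or all of this may fit.

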5.1.3 Safety Measures

Safety measures will be applied, as described below, to minimize risks associated with drug-assisted therapy sessions. The co-therapist or PI will be available via mobile phone or pager throughout the study to ensure subject safety.

Safety measures, including vital signs and a measurement of psychological distress, will be assessed during all experimental sessions. Subjects will rate their current degree of subjective distress with the SUD scale, which is a single-item self-report scale. The SUD will be completed repeatedly during the experimental sessions, with the degree of distress marked along seven points. Results of the SUD are intended to assist therapists in maintaining subject safety during experimental sessions.

The therapists will assess general wellbeing during each preparatory session, on each integrative session and during integrative telephone calls for seven days. Results of this scale are intended to assist therapists in maintaining subject safety throughout the treatment period of the study.

The C-SSRS is a clinician-administered measure of suicidal behavior devised to detect potential suicidal thoughts or behaviors during a clinical trial [154]. It consists of a Baseline form that assesses lifetime suicidal ideation, ideation intensity and behavior, and a form for assessing current suicidal ideation and behavior. The C-SSRS consists of a series of questions, and can be administered during a face-to-face interview or over the telephone. Suicidality will be assessed at Baseline, once during any face-to-face visit, during the second and seventh days of integrative telephone contact, and twice during each experimental session. Subjects who are discontinuing medication to participate in the study will complete the C-SSRS before and after medication washout. The C-SSRS

data will be collected on Case Report Forms (CRFs) for all administrations except for the second integrative session, unless the therapists observe an increase in suicidality. C-SSRS data from the second integrative session after each experimental session will be kept with the subject's Source Record.

Cardiovascular effects will be assessed via blood pressure and pulse measurement. Blood pressure and heart rate will be assessed periodically during each experimental session by an automatic blood pressure and pulse monitor. Blood pressure and pulse will be measured at the outset of the experimental session, once approximately every hour, or as needed. More frequent measures will be taken if there are symptoms, such as chest pain, shortness of breath, or neurological symptoms that may be indicative of hypertension. The therapists will measure subject body temperature approximately every 60 to 90 minutes. The timing of these measurements will be adjusted so that they do not interfere with the therapeutic process.

All AEs and spontaneously reported reactions will be collected, as described in Section 8.5. AEs and spontaneously reported reactions may be collected during face-to-face visits or over the telephone. Common reactions that are spontaneously reported are collected for seven days after each experimental session on a separate CRF page and will be categorized as mild, moderate, or severe.

As an additional safety and support measure, all subjects will be required to designate a family member, close friend, or significant other who knows them well to provide ongoing support for the duration of their active participation in the study. Precedence for the importance of post-session support has been established in earlier similar studies [155]. Responsibilities of the designated support person include:

- Providing reliable transportation, as required, to and from pre- and post-session appointments and participating in study visits, as appropriate.
- Driving the subject home or to another secure location following sessions. No participant will be allowed to drive themselves home after experimental sessions.
- Remaining available to attend to basic comfort needs and to talk with subject in person, by phone, or online for 24 hours post-session.

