3.3 Safety Objectives

The safety objectives of the study are to monitor and assure safety of subjects during and after the experimental sessions by assessing physiological effects, psychological distress, adverse events, spontaneously reported reactions and suicidality.

- Vital signs (BP, HR, BT) will be measured at baseline and every hour during experimental sessions until they return to baseline.
- Participant distress will be measured by the Subjective Units of Distress (SUD) scale at baseline and every hour during experimental sessions until return to baseline.
- Risk of suicide will be measured by the Columbia Suicide Severity Rating Scale (C-SSRS) during all in person visits, as well as twice during each experimental session at two hours after drug administration and the end of the experimental session, and on Day 2 and Day 7 after each experimental session.
- SAEs and AEs will be assessed throughout the study and spontaneously reported reactions, defined as expected AEs, will be assessed during each experimental session and for seven days after each experimental session, or until resolution.
- In addition to spontaneously reported reactions, symptoms specific to the study population will be collected at baseline and tracked throughout the study

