8.10.4 Safety Analyses

The primary measure of safety will be the reporting of adverse events. The Adverse events considered are Treatment Emergent Adverse Events (TEAE) defined as those AE's that occurred after dosing and those existing AEs that worsened during the study. Verbatim terms on case report forms will be mapped to preferred terms and system organ classes using the MedDRA dictionary. For incidence reporting if a subject has more than one adverse event mapped to the same preferred term, that adverse event will be reported only once using the highest severity and closest relationship to study drug. Subject incidence of adverse events will be displayed by Stage I treatment group and by system organ class. Adverse events will also be summarized by severity and relationship to study drug. Subject incidence of serious adverse events by Stage I treatment group will also be displayed. In addition to the listing of all adverse events, a listing of serious adverse events and a listing of adverse events leading to discontinuation of study drug will be included.

Summary tables of frequency listings of expected adverse events (Spontaneously Reported Reactions) mapped to preferred terms will be displayed during and after each experimental session by Stage I treatment group.

Columbia Suicide Severity Rating Scale (C-SSRS)

Suicidal ideation and behavior will be summarized according to suggestions made in the Columbia-Suicide Severity Rating Scale Scoring and Data Analysis Guide [3]. A positive response for suicidal ideation is counted when a subject answers "yes" to any one of the five suicidal ideation questions (Categories 1-5) on the C-SSRS, i.e. a score > 0 for suicidal ideation score. Serious suicidal ideation is a suicidal ideation score of 4 or 5. A positive response for suicidal behavior occurs when a subject answers "yes" to any one of the five suicidal behavior questions (Categories 6-10) on the C-SSRS, i.e. a score > 0 for suicidal behavior score. The number and percent of positive responses of Positive Ideation, Serious Ideation, and Positive Behavior will be tabulated by Stage I treatment group and time period. Compare lifetime serious suicidal ideation and positive behavior frequencies to cumulative frequencies anytime during the study until end of stage 1 and stage 2.

Subjective Units of Distress (SUD)

Descriptive statistics for SUD scores will be calculated by Stage I treatment group and time period with counts and percentages.

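### C-SSRS forms from the second integrative session reach the database only when therapists see an increase, yet the SAP tabulates percentages of any positive response without excluding those visits

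*Protocol*

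**What the plan says.** **Administration.** Protocol 5.2.6, on the biweekly sessions, states: "The C-SSRS will be administered just prior to beginning each integrative session". Tables 2 and 3 tick the scale at V8, V12, V17 and V21, each the second integrative session after an experimental session. The safety objective in SAP 3.3, like Protocol 3.3, asks for the C-SSRS "during all in person visits, as well as twice during each experimental session".

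**Recording.** Protocol 5.1.3 sends C-SSRS data to the CRF "for all administrations except for the second integrative session, unless the therapists observe an increase in suicidality", and adds: "C-SSRS data from the second integrative session after each experimental session will be kept with the subject's Source Record". It gives no reason for the exception and does not say what an increase is measured against.

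**Analysis.** SAP 8.10.4 plans this summary: "number and percent of positive responses of Positive Ideation, Serious Ideation, and Positive Behavior will be tabulated by Stage I treatment group and time period". Positive ideation is defined as "a score > 0 for suicidal ideation score". The SAP also compares lifetime serious ideation and behavior with "cumulative frequencies anytime during the study until end of stage 1 and stage 2". It does not mention the recording exception, define a time period or give a denominator. SAP 8.4 has the safety analyses use all available data. SAP 8.2 deals only with early-termination visits. Protocol 19.0 requires every analysis to be run on the sponsor's monitored database.

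**The concern.** Whether a value is recorded depends on the value itself, and the recording trigger differs from the analysis criterion. The CRF rule asks whether suicidality has risen; the SAP asks whether any is present. Subjects with steady or declining ideation fall between the two. They are positive by the SAP's definition, and a form has been completed, but nothing reaches the database from which the table is made.

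Protocol 12.0 presents the trial as chiefly about safety, and suicidality is one of its named safety objectives. With arms of 8 and 4, one unrecorded positive subject moves a whole-arm visit percentage by 12.5 or 25 points. A reader of the safety table would have no sign that the entries for these visits had been selected.

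**Working it through.** The documents state no C-SSRS rate, so there is no planned figure to reproduce. The check counts the affected forms and then follows assumed results through the recording rule.

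**Step 1: affected administrations.** Allocation is 8 MDMA and 4 placebo.
- Stage 1: 12 subjects × 2 visits = 24 (8 × 2 = 16 on MDMA, 4 × 2 = 8 on placebo).
- Stage 2: at most 4 × 2 = 8.
- Total: 24 + 8 = 32 at most.

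**Step 2: share of the schedule.** Taking Table 2 with its footnotes, the C-SSRS from V6 to V14 falls at V6 (twice), Day 2 call, Day 7 call, V8, V9, V10 (twice), Day 2 call, Day 7 call, V12, V13 and V14. That is 13 administrations per subject, and 2/13 = 15% are under the exception.

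**Step 3: the gap in full capture.** The visits run 1 day, then 2 weeks, then 2 weeks after the session, so V9 is at about day 1 + 14 + 14 = 29. From the Day 7 call to V9 is 29 − 7 = 22 days, about three weeks. Within that interval, the scheduled C-SSRS result reaches the CRF only if it is judged an increase. The same holds between the second Day 7 call and V13.

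**Step 4: effect on a visit-level percentage.** Let n be the arm size, k the number truly positive at the visit, and i the number of those judged an increase. Assume that every subject is assessed and that every recorded increase scores as positive. Then:
- true percentage = k/n
- database count over the whole arm = i/n
- database count over recorded forms = i/i (undefined if i = 0)

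| Arm | k | i | True | Whole-arm denominator | Recorded-form denominator |
|---|---|---|---|---|---|
| MDMA, n = 8 | 2 | 1 | 25.0% | 12.5% | 100% |
| MDMA, n = 8 | 2 | 0 | 25.0% | 0% | undefined |
| MDMA, n = 8 | 3 | 1 | 37.5% | 12.5% | 100% |
| MDMA, n = 8 | 2 | 2 | 25.0% | 25.0% | 100% |
| Placebo, n = 4 | 2 | 1 | 50.0% | 25.0% | 100% |

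The whole-arm figure is too low whenever i < k. The recorded-form figure is too high whenever i ≥ 1 and k < n. The values of k and i are assumptions chosen to show the mechanism.

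**Step 5: the cumulative comparison.** This covers serious ideation and behavior only, at any time on study. A new or worse state at V8 triggers CRF entry. An unchanged serious state would ordinarily have been recorded at V6 or at the Day 2 or Day 7 call, and would be picked up again at V9 if it continued. V12 is bracketed in the same way by V10, its two calls and V13. A subject is lost only in a narrow pattern. One example is serious ideation that is absent at the neighbouring contacts, returns to its pre-treatment level at V8, and is not called an increase because the comparison is with baseline.

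**The case against.** The case for leaving this alone is that the exception is explicit and looks deliberate, and that nobody goes unassessed. The scale is given and the result is kept in the Source Record. SAP 8.10.4 makes adverse event reporting the main safety measure, and the C-SSRS is a descriptive table with no test. Protocol 8.5 collects adverse events involving psychiatric change throughout, so clinical worsening has a second route to the database. No text says that V8 or V12 will have its own row, and no text uses recorded forms as the denominator, so the 100% figure depends on a choice the SAP has not made.

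Most of this stands and limits the point, but it does not remove it. The second route catches worsening, whereas the forms being lost are those of subjects who are positive and not worse. Pooling visits into a period would dilute the selection, since neighbouring contacts would often show the same ideation, but the selectively captured forms would still be in the pool. Leaving the denominator open settles nothing: with some stable ideation present, the whole-arm choice undercounts, and the recorded-form choice generally overstates.

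Three stronger readings are tempting, and the documents do not support them:
- A reader might infer that persistent ideation disappears from the cumulative counts. Non-serious ideation was never part of that comparison, and serious ideation is bracketed by contacts recorded in full.
- A reader might infer that wrong visit-level percentages are certain to be published. Since the SAP does not define a time period, that is only a possibility.
- A reader might infer that recording will differ by arm, because the therapists who judge the increase may guess the assignment. Protocol 5.1.4 collects those guesses, but nothing shows that they would influence recording.

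**Conclusion.** The point holds as a mismatch between the recording rule and the planned table. At one visit per treatment cycle, capture depends on an observed increase, while the SAP counts presence. Neither document reconciles the two, and the database requirement in Protocol 19.0 leaves the Source Record forms out of the planned analysis.

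Its reach is limited: up to 32 forms, or 2 of 13 scheduled administrations per subject between V6 and V14, in a descriptive safety summary. The direction of error depends on the denominator that is chosen. Its size depends on how many subjects have stable ideation, which the documents do not say. The primary LSAS analysis is untouched. The correction is worth making because the omitted data already exist and cost little to include.

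**What to change.** **Preferred.** Delete the exception in Protocol 5.1.3 and enter every C-SSRS form from V8, V12, V17 and V21 on the CRF. With all subjects on study and assessed, the visit percentages then become k/8 and k/4, with no selection. The cost is data entry of at most 32 extra forms, all of them already completed, and a minor protocol amendment with its review.

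**Fallback.** If the exception stays, SAP 8.10.4 should leave these visits out of the by-period C-SSRS table, say why, and use the number of subjects assessed in each period as the denominator. Increases recorded at these visits should still be listed and still count in the cumulative comparison. This costs a few sentences in the SAP and needs no protocol change, but it leaves the stable positive responses unreported.

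Under either option, the SAP should define the time periods.
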